| Intervention | For every adult (a "case") tested positive by RTqPCR, up to 45 mL of blood will be taken, a nasal swab and an oropharyngeal swab will be performed, an induced sputum (or saliva), hair sample and a stool samples will be recovered at the inclusion. As follow-up, 6 months, 15 months and 24 months after inclusion, the same sampling will be performed. Two additional sampling visits will be proposed to adult participants with a reinfection or a post-vaccination infection at 3 weeks and at 2 months. For every child tested positive by RTqPCR, up to 50 mL of blood will be taken, a nasal swab, oro- and naso-pharyngeal swabs, induced sputum or saliva, hair sample, as well as a stool sample will be obtained at inclusion. The follow up visits at 6, 15 and 24 months after inclusion, will include the same samples. For patients at home, an experienced nurse from CIEC will perform the sampling, using all the required precautions and protections in the actual context. For hospitalised patients, a simplified sampling strategy will be put in place and adapted to the patient state, the workload of staff and adapted constantly depending on the evolution of the epidemy. Below is described the maximal sampling strategy. |
| Study timelines | 
 ● Recruitment period: up to 29 months (March 2020-August 2022) - to be adapted to the evolution of the epidemiological situation) First patient in: March 2020 ● Follow-up period : max 24 months ● Analysis of results and study report: 3 months ● Global duration: 54 months (to be adapted on the duration of the epidemiological situation) |
| Population | Predi-COVID Inclusion criteria: |

| | |
|--|---|
| | 
 • Signed informed consent form • Adult (≥ 18 years old), child and adolescent (0-17 years old) patients with confirmed SARS-CoV-2 infection as determined by PCR, performed by one of the certified laboratories in Luxembourg • Hospitalized or at home 
Exclusions criteria :
 
 • Patients not understanding French or German • |
| Patient withdrawal criteria | Transfer outside Luxembourg if no information can be collected in the receiving country. |

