2.2 Rationale

The pathogen for the new outbreak has been identified as a novel enveloped RNA betacoronavirus2 that has currently been named severe acute respiratory syndrome coronavirus 2 (SARS-CoV-2), which has a phylogenetic similarity to SARS-CoV (1). Studies on epidemiological and clinical characteristics of patients with COVID-19 show that compared to women, men are more infected and the median age is 49.0 years (1, 4). Common symptoms at onset of illness are fever, cough, dyspnoea and myalgia or fatigue; less common symptoms were sputum production, headache, haemoptysis and diarrhea. Complications included acute respiratory distress syndrome, anaemia, acute cardiac injury and secondary infection (4). The risk for serious disease and death in COVID-19 cases increases with age (5). In the United States case-fatality percentages increased with increasing age, from no deaths reported among persons aged ≤ 19 years to highest percentages (10%–27%) among adults aged ≥ 85 years (5). The findings from the United States are similar to data from China, which indicated $>80\%$ of deaths occurred among persons aged ≥ 60 years (5). As of 19 March 2020, no vaccine has been successfully developed for COVID-19. The treatments are mainly symptomatic and supportive. The study by Huang et al. reported that the most common complications in patients with 2019-nCoV infection were acute respiratory distress syndrome, followed by anemia, acute heart injuries, and secondary infections.

Due to the rapid spread of COVID-19, we determined that identifying profiles of patients predictive of more severe prognosis would be key to clinical management and would support more efficient public health measures. Although there have been some studies on epidemiological and clinical characteristics of patients with COVID-19, there is a lack of research investigating the prognostic factors for the severity of the disease. The accurate prognostic evaluation of COVID-19 can provide a guiding basis for active and effective management of the outbreak.

The purpose of this project is the identification of patients clinical and socio-demographic characteristics as well as pathogen and/or host predictive biomarkers for the severity of the disease. We are aiming to better understand the heterogeneity observed in disease severity through a stratification approach of the cohort in Luxembourg.

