7.3 Ancillary study: Predi-COVID-H

The samples and data collected during the study course are described in the table below. The Predi-COVID-H participants will be able to participate either to data collection only or to both data and sample collection. For sample collection they can choose to do all or part of the sampling. Since the national recommendations for the follow-up of contact persons of positive cases have recently changed with the prescription of a PCR test 5 days after the test of the case person, we adapted our sampling strategy with a follow-up visit conditioned by the PCR test result.

| Predi-COVID-H | | | |
|--|---|--|--|
| | Inclusion | Follow-up | |
| | | If RTqPCR prescribed by Sanitary Inspection results = negative | If RTqPCR prescribed by Sanitary Inspection results = positive |
| Informed consent | X (e-consent for data collection and written consent for sample collection, but stored electronically) | | |
| Data collection : online questionnaires (for adult participants and children > 10 years) | | Data collection daily for up to 14 days | |
| CoLive LIH application (optional, for adults and children >10 years) | | Regular voice recordings + short questionnaires | |

| | | | |
|--|---|--------------|--|
| Blood sample : up to 50mL (for children, volume adapted to child's weight) | X | X (6 months) | |
| Nasopharyngeal swab | x | x (6 months) | |
| Oropharyngeal swab | x | x (6 months) | |
| Stools | x | x (6 months) | |
| Hair sample | x | x (6 months) | |
| Sputum/saliva | x | x (6 months) | |
| End of study | | | X (contacts with positive PCR will be proposed to be enrolled in the Predi-COVID cohort and to start the follow-up at inclusion visit Predi-COVID) |

➤ **Predi-COVID-H biological characterization (according to sample type) (not exhaustive)**

Blood sample :

- **Antibodies to SARS CoV2**
- Immunophenotyping
- TRC repertoire
- Antibodies to CoV OC43, NL63 and 229E (optional)

Stool :

- SARS-CoV-2 and other CoV specific RT-PCR
- Microbiome-omics

Sputum/saliva :

- cell number, eosinophilic cationic protein, IL8, fibrinogen (optional)

Hair :

- hormones/glucocorticoid concentration

Swabs :

- SARS-CoV-2 and other CoV specific RT-PCR
- Molecular diagnosis for rhinovirus, adenovirus, picornavirus, RSV, influenza A and B, parainfluenza 1-3, human metapneumovirus, *M. pneumoniae*, *C. pneumoniae*, *L. pneumophila*
- Sequencing of viral PCR targets for confirmation and identification of mutations

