11.4 Statistical analyses

Descriptive statistics will be produced for the main endpoints, namely hospitalisation, intensive care / resuscitation admission, ventilation, their duration, death and severity of the disease. Secondary endpoints together with other variables including potential prognostic factors of the disease will also be described with mean (+- STD) or frequencies (%) as adequate.

A logistic model will be used to study whether the risks of hospitalisation, intensive care admission or intubation as well as death are associated with a specific risk factor. adjustment will be done on age, gender and other potential confounding factors.

Factors triggering the severity of the disease will be evaluated with a Mantel-Haenszel chi square to evaluate if different levels of patients' characteristics are associated with a more serious form of the disease.

Further stratification of the patient cohort will be performed through Machine learning techniques to include biological and other omics measurements. A deep phenotyping related to the symptoms of the disease as well as biosampling allowing for laboratory-based and computational analytics will be performed. The stratification approach will include data-driven tools and allow to define disease trajectories that will be translated into clinical and/or biomarker-defined subgroups

The time to conversion from the PREDI-COVID-H cohort to the PRECOVID cohort will also be studied.

[figure not shown]
Missing data will not be replaced concerning the endpoints. A replacement method such as multiple imputations through chained equations will be envisaged for the other variables and risk factors.

The limits of the study linked to the size of the sample enrolled, the extent of the effects or the selection of participants and other potential limits will be evaluated and discussed.

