| Si oui: Quel type de test a été fait? (PCR, Rapid LAMP test, test antigénique rapide/test sérologique / ne sait pas) |
| Si oui: Au moment des tests aviez-vous des symptômes? |
| Si oui: Avez-vous été hospitalisé pour Covid-19? |
| Si oui: Un membre de votre foyer a-t-il été testé positif pendant cette même période? |
| Si oui: Quel est l'âge des membres du foyer testés positifs (vous inclus) |
| Participez-vous ou avez-vous participé à une autre étude en lien avec Covid-19? (SéroCov2, Convince, Prédicovid, Orchestra, Cov-Escape, autre?) |

Vaccination

| | |
|-------------------------------------|---------|
| Etes-vous vaccinés contre COVID-19? | oui/non |
|-------------------------------------|---------|

| | |
|---|--|
| Si oui: quand?(dates doses) | |
| Si oui zone de vaccination | |
| Si oui : Connaissez-vous la marque de vaccin? | |
| Si 2nd dose pas faite, raison? | |
| Si oui: Avez-vous eu des effets secondaires après la vaccination? | |
| Si oui: Spécifier le type d'effets secondaires : | |
| Réactions au niveau du site d'injection : | Oui/Non |
| rougeur | Oui/Non |
| chaleur | Oui/Non |
| douleur | Oui/Non |
| démangeaisons | Oui/Non |
| hématome | Oui/Non |
| gonflement | Oui/Non |
| induration | Oui/Non |
| ecchymose | Oui/Non |
| sensibilité | Oui/Non |
| Effets secondaires systémiques : | |
| Avez-vous eu un gonflement important des membres? | oui/non |
| Fièvre | oui/non |
| Frissons | oui/non |
| Maux de têtes | oui/non |
| Nausée/vertige | oui/non |
| Augmentation soudaine de fatigue / Malaise | oui/non |
| Douleurs musculaires | oui/non |
| Douleurs articulaires | oui/non |
| Réaction cutanée (éruption, peau qui brûle..) | oui/non |
| Arythmies | oui/non |
| Myocardites | oui/non |
| Péricardites | Oui/non |
| Autre effet indésirable? spécifier | oui/non |
| Si oui après dose 2, combien de temps a duré cet effet indésirable? | Less than 1 day / 1 day / 2 days / 3 days / 4 days / 5 days / 6 days / 1 week / 2 weeks / 1 month / Still unresolved |

| | |
|---|--|
| Si oui après dose 1, combien de temps a duré cet effet indésirable? | Less than 1 day / 1 day / 2 days / 3 days / 4 days / 5 days / 6 days / 1 week / 2 weeks / 1 month / Still unresolved |
| Date des premiers effets indésirables après dose 1 | |
| Date des premiers effets indésirables après dose 2 | |
| Avez-vous été vacciné contre la grippe saisonnière? | oui / non / ne sais pas |
| Si oui date de vaccination | |

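### Clinical severity is tested with a Mantel-Haenszel chi-square that names no stratifier, and it is not among the outcomes of the age- and gender-adjusted models

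*Protocol*

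**What the plan says.** Protocol section 11.4 plans two association analyses.

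- **Logistic model.** "A logistic model will be used to study whether the risks of hospitalisation, intensive care admission or intubation as well as death are associated" (the predictor being some chosen risk factor). On covariates it adds that "adjustment will be done on age, gender and other potential confounding factors". The synopsis describes models for the same outcomes with the same adjustment and does not mention the Mantel-Haenszel test.
- **Mantel-Haenszel test.** In a separate paragraph: "Factors triggering the severity of the disease will be evaluated with a Mantel-Haenszel chi square", the purpose being "to evaluate if different levels of patients' characteristics are associated with a more serious form of the disease". No stratum or covariate is named.

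Section 4.1 lists clinical severity as a main criterion separate from hospitalisation, intensive care, ventilation, transfer and death. Section 11.4 also lists it separately among the main endpoints.

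Other relevant statements:

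- Section 2.2: "The risk for serious disease and death in COVID-19 cases increases with age".
- Sections 6.1 and 11.3: participants are eligible from age 0 upward, and everyone enrolled is analysed.
- Synopsis: "Recruitment period: up to 29 months (March 2020-August 2022"). Section 2.2 notes that no vaccine existed at the start, and section 2.5 names variants, waves and infections before and after vaccination as open questions.
- Annex 3 collects earlier positive tests and vaccination ("Etes-vous vaccinés contre COVID-19"), with dates.

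**The concern.** The principal objective in section 3.1 is to find characteristics associated with severity. For the criterion that carries that name, the only association analysis stated is one for which no control of confounding is described, although the preceding paragraph does describe it for other outcomes.

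The term Mantel-Haenszel chi-square covers both a test combined over strata and an unstratified one-degree-of-freedom trend test. A comparison of levels of a characteristic with a more serious form of disease, with no strata named, reads as the second.

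Comorbidities, regular medication and many immune markers vary with age. An unstratified test would credit part of the age effect to them. The bias does not shrink with recruitment. Section 11.2 wants as many participants as feasible, and a larger sample makes a spurious association more likely to reach significance.

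**Working it through.** The plan gives no figure for this test, so there is none to reproduce. The risk ratio (RR) of 2 in section 11.2 serves only as a yardstick. The documents give no age mix, no severity risk by age and no factor prevalence. All of these are assumed below.

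**Step 1. Crude association with no effect inside age groups.** Let *w* be the share of older participants, *r* the severe risk and *e* the factor prevalence (Y younger, O older).

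Risk if exposed = [(1−w)·eY·rY + w·eO·rO] / [(1−w)·eY + w·eO]. The risk if unexposed uses 1−e in place of e.

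Worked case: w = 20%, r = 4% and 20%, e = 10% and 40%.

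- Exposed: (0.08×0.04 + 0.08×0.20)/0.16 = 0.0192/0.16 = 12.0%.
- Unexposed: (0.72×0.04 + 0.12×0.20)/0.84 = 0.0528/0.84 = 6.29%.
- Crude RR = 12.0/6.29 = 1.91. Crude odds ratio (OR) = (0.12/0.88)/(0.0629/0.9371) = 2.03.

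| Older share | Risk, younger / older | Factor, younger / older | Crude RR | Crude OR |
|---|---|---|---|---|
| 20% | 4% / 20% | 10% / 40% | 1.91 | 2.03 |
| 20% | 3% / 25% | 10% / 40% | 2.28 | 2.49 |
| 30% | 5% / 20% | 15% / 40% | 1.53 | 1.61 |

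The true RR within each age group is 1 throughout.

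**Step 2. False-positive rate.** Simulation with 5,000 runs per cell at two-sided 5%: 30% older, overall severe risk 7%, factor present in 20% of younger and in 40% or 60% of older participants, no effect within age groups. Each range runs from 40% to 60% prevalence in the older group.

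| Older vs younger severity RR | Crude RR | Unstratified, N=200 | Unstratified, N=1000 |
|---|---|---|---|
| 2 | 1.18 to 1.33 | 6.8% to 8.5% | 11.0% to 23.1% |
| 4 | 1.38 to 1.76 | 10.7% to 21.1% | 27.4% to 68.5% |
| 8 | 1.57 to 2.21 | 15.0% to 36.4% | 48.6% to 92.1% |

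Stratified by age, the same test rejects in 4.3% to 5.8% of runs in these cells. When age is unrelated to the factor or to severity, the unstratified test rejects in 3.8% to 5.5% of runs, so there is no inflation.

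**Step 3. Range.** Steps 1 and 2 together give a spurious crude RR of 1.18 to 2.28. Period and vaccination would work by the same mechanism if linked to both the factor and severity, but they were not simulated.

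**Step 4. Room for covariates.** If the 7% in section 11.2 is read as severe risk (the text does not make clear what it is a prevalence of), 200 adults give 200×0.07 = 14 severe cases and 100 children give 7. This limits how many covariates or strata the sub-samples can carry.

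**The case against.** The strongest reply is that the protocol never says the test is unadjusted. It names no stratifier, a Mantel-Haenszel test can be stratified by age, and a statistical analysis plan that is not shown may name the strata. This stands as a limit on the claim: a reader might infer that an age-free test has been fixed, and the text does not go that far. It does not remove the point, because the protocol chooses the test, says where adjustment applies, and leaves severity outside it.

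Second, much of severity is already covered. The synopsis evaluates it through hospitalisation, intensive care, oxygen, ventilation, transfer and daily activities, and several of these are outcomes of the adjusted models. This also stands. What remains uncovered is clinical severity as its own criterion, together with supplemental oxygen, transfer and daily activities.

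Third, *triggering* might be taken as a declared causal reading. The same sentence goes on to speak of association, as does section 3.1, so it is loose wording.

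Fourth, a reader might infer that vaccination goes unused. The logistic model's open-ended list of confounders could include it, and the secondary objectives in section 3.2 deal with vaccination and reinfection directly. It is simply not named in 11.4.

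Finally, because "contacts with positive PCR will be proposed to be enrolled in the Predi-COVID cohort", a reader might infer that shared households seriously distort the test. The documents do not support this. Enrolment of converted contacts is only offered, their number is not given, and for individual-level factors the effect is small. If 20% of participants are in two-case households and the intraclass correlation is 0.3 for both outcome and factor (all assumed), the design effect is 1 + 0.2×0.3×0.3 = 1.018, and a 5% test runs at about 5.2%.

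**Conclusion.** The point holds in a limited form and is worth correcting before analysis. Section 11.4 leaves clinical severity without a stated adjusted association analysis, and the test it assigns reads as unstratified. If it is run that way, characteristics linked to age can appear as severity factors with no effect of their own.

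Under the assumed inputs the spurious crude RR is about 1.2 to 2.3, so at the upper end it matches the RR of 2 in section 11.2. The false-positive rate is 6.8% to 36.4% at 200 participants and 11.0% to 92.1% at 1,000. These figures require an unstratified test and a factor related to age. They do not show that every characteristic would be declared a severity factor, or that false findings are certain. Confounding by calendar period or vaccination is plausible over recruitment of up to 29 months but has not been quantified.

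**What to change.** In section 11.4:

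1. Add clinical severity to the outcomes of the adjusted regression: ordinal if it is graded, logistic if it is binary.
2. Adjust for age and gender, and for calendar period and vaccination or prior-infection status where event numbers allow. Use penalised estimation in the sub-samples.
3. Keep the Mantel-Haenszel test as descriptive, or stratify it at least by age.
4. Replace *triggering* with *associated with*.

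Household-robust standard errors can be an optional sensitivity analysis if household links are available. The annexes shown ask about household size and positive household members but contain no household identifier.

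The cost is a few sentences in 11.4. Age, sex, inclusion date, vaccination and earlier positive tests are already in the data collection. The downside is a few more parameters where events are sparse, which is why period and vaccination are conditional on event numbers.

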| 
Ancillary study
 | 
An ancillary study will be added (Predi-COVID-H). For patients included as well as subjects living with positively tested patients on the basis of a volunteer informed consent.
 
Predi-COVID-H is an ancillary cohort study composed of Household members of index cases to monitor symptoms and disease outbreak in this high-risk population. For every asymptomatic member of the family of a “case” included in the Predi-COVID sub-sample (a “contact”), clinical as well as socio-economic characteristics will be collected. Biological samples will also be collected at the same time as the “case” visit by nurses and up to 50 ml of blood, nasopharygeal and oropharyngeal swabs, stool, saliva and hair samples will be taken at baseline for adults and children. According to the new recommendations of the Health Directorate, all Household contacts of positive cases are invited by the Sanitary Inspection to be tested 5 days after the diagnostic test of the “index case”. In case of positive result, the “contact” will be proposed to be enrolled in the Predi-COVID study. Otherwise, a second visit will be planned 6 months later, to collect blood, nasopharygeal and oropharyngeal swabs, stool, saliva and hair samples. All “contacts” will be followed digitally.
 
Predi-COVID-H inclusion criteria:
 
 ● Adult and children (0-17 ans) house members of COVID-19 positive participants. 
Exclusions criteria :
 
 ● Patients not understanding French or German 
Sample size: A minimum of 100 participants (adults and children) will be included in the sub-study on house-members. The sample size and the sampling strategy may have to be adapted to the rapidly evolving knowledge on COVID-19.
 |
|-------------------------------|--|

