ANNEX 5 :

QUESTIONNAIRE PREDI-COVID-H

Utilisation du module e-PRO de Ennov Clinical

Questionnaires français

V1.0

Suivi à distance depuis un smartphone, tablette ou ordinateur :

- 1 questionnaire court par jour tant qu'il n'y a pas eu de confirmation de Covid19 par test positif et pendant 14 jours

Table des matières

[Système d'alerte](#)

[Questionnaire quotidien](#)

[Questionnaire permanent](#)

[Profil](#)

Questionnaire quotidien

Mon état de santé général

Vous êtes un membre du foyer d'une personne diagnostiqué positif à Covid19. Veuillez remplir ce questionnaire de suivi quotidien.

1) Date du questionnaire :

2) Avez-vous été testé et diagnostiqué positif à Covid19 ? Oui/Non

3) Vous êtes: A la maison / A l'hôpital / Autre

Si A l'hôpital : Lequel : menu déroulant

Centre Hospitalier de Luxembourg / Fondation Hôpitaux Robert Schuman / Centre Hospitalier Emile Mayrisch / Centre Hospitalier du Nord / Autre

4) Comment vous sentez-vous aujourd'hui ? Je me sens bien / Je me sens fatigué(e) / Je me sens mal

5) Avez-vous bien dormi ? Oui/Non

Si non, pourquoi ? [Champ libre]

6) Avez-vous une toux sèche ? Oui/Non

7) Avez-vous une augmentation de votre toux habituelle ces derniers jours ? Oui/Non

8) Avez-vous un mal de gorge apparu ces derniers jours ? Oui/Non

9) Avez-vous noté une forte diminution ou perte de votre goût ou de votre odorat ? Oui/Non

10) Avez-vous de la diarrhée ? Avec au moins 3 selles liquides/molles par jour. Oui/Non

11) Avez-vous des douleurs musculaires ou des courbatures inhabituelles ces derniers jours ? Oui/Non

12) Avez-vous des douleurs thoraciques ces derniers jours ? Oui/Non

13) Quel est votre niveau de douleur actuel ? (Notez de 1 à 10)

14) Avez-vous de la fièvre ? Oui/Non

Avez-vous un thermomètre ? Oui/ Non

Si oui, Veuillez prendre votre température :

15) Avez-vous des difficultés respiratoires ? Oui/Non

16) Avez-vous vu apparaître une gêne respiratoire ou une augmentation de votre gêne respiratoire habituelle ? Oui/Non

17) Quel est votre poids ? (se peser sans chaussure) __ kg ou Je ne sais pas

18) Avez-vous des difficultés importantes pour vous alimenter ou boire ? Oui/Non

19) Avez-vous d'autres symptômes ? Oui/Non

Si oui, veuillez préciser lesquels : [champ libre]

Questionnaire permanent

A ne remplir qu'une fois

Profil

-
- Sexe
- Date de naissance
- Poids (kg)
- Avant le diagnostic de Covid19, avez-vous perdu, sans le vouloir, 3 kg ou plus dans les 6 derniers mois ? (Oui/non)
- Taille (cm)

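### The household analysis counts a move into Predi-COVID rather than infection, so contacts who decline re-enrolment drop out of the event count and contacts infected at entry are not set aside

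*Protocol*

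**What the plan says.** Section 11.4 of the protocol states: "The time to conversion from the PREDI-COVID-H cohort to the PRECOVID cohort will also be studied". It is the only analysis named for Predi-COVID-H, and the event is a change of cohort.

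The route between the cohorts is set out elsewhere:

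- **Trigger.** The Synopsis says that "all Household contacts of positive cases are invited by the Sanitary Inspection to be tested 5 days after the diagnostic test" of the index case. Section 7.3 says the sampling plan was adapted to this test.
- **Transfer.** In the Section 7.3 table a positive PCR ends participation in Predi-COVID-H, and "contacts with positive PCR will be proposed to be enrolled in the Predi-COVID cohort", restarting at its inclusion visit. The Synopsis also words this as an offer. Section 13.1 provides a separate information sheet and consent form for each cohort.
- **Entry.** The inclusion criterion in the Synopsis is "Adult and children (0-17 ans) house members of COVID-19 positive participants". The descriptive text there calls contacts asymptomatic, but no negative test is required.
- **Other data on infection.** Section 7.3 lists SARS-CoV-2 RT-PCR among the assays on contacts' swabs, which are taken at baseline and 6 months. The daily questionnaire in Annex 5 asks "Avez-vous été testé et diagnostiqué positif à Covid19" for up to 14 days.
- **End of follow-up.** Contacts with a negative PCR have a 6-month visit (Synopsis, Section 7.3). Section 8 discontinues contacts after one week if they are seronegative and symptom free.

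**The concern.** The Synopsis gives the purpose of Predi-COVID-H as following symptoms and the spread of disease in households. That calls for an infection event. Cohort transfer differs from infection in three ways:

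1. It depends on the contact agreeing to a second study, so acceptance is built into the endpoint.
2. In the described pathway it hangs on one PCR at a fixed point after the index case's test. A later positive becomes an event only if the contact enrols by another route.
3. It does not separate infections present at entry from those acquired afterwards, although only the latter are conversions in someone at risk.

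A reported time to conversion would therefore mix infection, willingness to re-enrol and the testing calendar. A total that looked about right could still be made up of the wrong people.

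**Working it through.** The protocol gives no figure to reproduce. The household minimum of 100 in the Synopsis comes without power, effect size or event rate. The check is a comparison of the texts, followed by an illustration.

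**Who becomes an event if Section 11.4 is followed as written**

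| Contact | Infected after entry? | Counted as a conversion? |
|---|---|---|
| Negative at entry, positive at the day-5 PCR, enrols | Yes | Yes |
| Negative at entry, positive at the day-5 PCR, declines | Yes | No |
| Negative at day 5, positive later, enrols by the general route (Section 6.4) | Yes | Yes |
| Negative at day 5, positive later, does not enrol | Yes | No |
| Already infected at entry, enrols | No | Yes, since nothing excludes them |

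Rows 2 and 4 lower the count and row 5 raises it.

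**Illustration of direction.** *N* = 100 is the Synopsis minimum. All rates are assumptions:

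- *p*: share infected at entry
- *i*: share of the rest newly infected
- *l*: share of new infections first positive after day 5
- *a*: share of positives who enrol

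Formulas:

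- True new infections = *N*(1 − *p*)*i*
- Counted, late positives all missed = *a*[*Np* + *N*(1 − *p*)*i*(1 − *l*)]
- Counted, late positives all reaching the offer = *a*[*Np* + *N*(1 − *p*)*i*]

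With *p* = 0.10, *i* = 0.20, *l* = 0.30, *a* = 0.70:

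- Infected at entry: 100 × 0.10 = 10
- True new infections: 90 × 0.20 = 18, of which 18 × 0.70 = 12.6 are found by day 5
- Counted, low: 0.70 × (10 + 12.6) = 15.8
- Counted, high: 0.70 × (10 + 18) = 19.6
- Share of counted conversions infected at entry: 10/22.6 = 44% (low count) and 10/28 = 36% (high count)

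The total looks close to 18, yet the low count contains only 0.70 × 12.6 = 8.8 of the 18 new infections.

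**Range.** The pairs (*p*, *i*) tried were (5%, 20%), (10%, 10%), (10%, 20%) and (20%, 10%), with *l* from 10% to 50% and *a* from 50% to 100%.

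- Lowest count against truth: *p* = 0.05, *i* = 0.20, *l* = 0.50, *a* = 0.50 gives 0.50 × (5 + 9.5) = 7.25 counted against 19 true.
- Highest count against truth: *p* = 0.20, *i* = 0.10, *a* = 1, late positives all counted, gives 20 + 8 = 28 counted against 8 true.
- Share infected at entry: from 5/24 = 21% to 20/(20 + 4) = 83%.

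**The case against.** The best defence is that Section 11.4 offers one exploratory sentence without a formal definition, and that a statistical analysis plan, not available here, may supply the time origin, at-risk set and censoring. Section 13.1 assigns people to cohorts by test status, so conversion could be shorthand for turning positive. The analysis serves no objective in Section 3 and no criterion in Section 4, and Section 11.4 already promises to discuss limits due to participant selection.

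Part of this stands. Operational detail can wait for an analysis plan, and the low rank of the analysis limits the consequences. But the protocol itself has chosen a cohort change as the event, and its own pathway makes that change optional. If turning positive is meant, the sentence should say so.

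A reader might go further than the documents allow in four places:

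- *All later positives are lost.* They are not. The contact diary asks about a positive test, swabs are taken for RT-PCR at 6 months, and under Section 6.4 everyone who tests positive is phoned about research. Later positives may be missed as conversions; they are not bound to be.
- *The endpoint understates infection by a known fraction.* If 20 of 100 contacts were infected and 25–50% refused, 15 to 10 would be counted. That only restates the assumed refusal rate and ignores infections present at entry.
- *Contacts infected at entry are certain to count.* The text does not say so. It contains nothing that would remove them.
- *Event times collapse to a single value.* That presumes a time origin, and none is stated. Day 5 runs from the index case's test, while contacts enter at a nurse visit whose timing relative to that test is not fixed.

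**Conclusion.** The point holds in a limited form. As worded, the household analysis measures acceptance of re-enrolment as well as infection, and it does not set aside contacts infected at entry. This follows from Sections 7.3, 11.4 and 13.1 and the Synopsis and needs no assumption.

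The size does need assumptions. Refusals and unenrolled late positives pull the count down, infections present at entry push it up, and the documents give no rate for any of these. Neither the direction nor the amount of the net bias can be stated. The illustration shows only that the count can fall well below or well above the true number, and that a near-correct total can hide a large share of infections present at entry.

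The wording should be corrected because it governs the ancillary cohort's only named analysis and most of the data for a better endpoint are already collected. It is a secondary matter, and the main severity objective does not depend on it.

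**What to change.** Reword the sentence in Section 11.4, and align the Synopsis, as follows:

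1. **Event.** First positive SARS-CoV-2 test in the contact, from the day-5 PCR, a positive test reported in the 14-day diary or another recorded positive, whether or not the contact enrols in Predi-COVID. Enrolment after a positive test can be reported separately as an acceptance rate.
2. **At-risk set.** Report contacts positive on the baseline swab separately and leave them out. Sampling is optional under Section 7.3, so contacts without a baseline sample need their own category.
3. **Timing.** State the time origin, and treat the infection date as lying between the last negative and first positive test.
4. **Follow-up.** Reconcile the one-week discontinuation in Section 8 with the 14-day questionnaires (Section 7.3, Annex 5) and the 6-month visit (Synopsis, Section 7.3). Until these agree, censoring cannot be defined.
5. **Antibodies.** Add seroconversion from baseline to 6 months in unvaccinated contacts only if their vaccination status will be available. The contact questionnaire in Annex 5, as shown, has no vaccination item; those items are in the Predi-COVID case report form (Annex 3).

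The cost is mainly redrafting, since most of the inputs are already collected. Timing becomes an interval instead of an exact day. Diary capture will be lacking in younger children, because questionnaires go only to adults and children over 10, and baseline status will be incomplete where samples are declined.
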